### 4.2 SAMPLE SIZE

PICANet data from 2014/15 indicates that the 30-day mortality rate for transported PICU admissions is approximately 7% and that transport teams reach critically ill children within 3 hours of referral acceptance in 85% of cases (the current target). We anticipate a sample of

15,000 transports over the three year time window of the DEPICT Study. Of the 15,000 transports we anticipate that approximately 12,750 (85%) will be made in less than 3 hours. The remaining 2,250 (15%) will be made in more than 3 hours. We have adequate power to detect a 3 percentage point reduction in mortality (7% to 4%). This sample is assuming that each transport and admission is a separate child, when in reality a single child may contribute multiple transports.

Adjustments will be made using the 'rule of thumb' of at least ten events per adjustment. For example, if we observed 400 deaths, we would make no more than 40 adjustments. However, we will work to ensure statistical parsimony by keeping the model as simple as practical.

## 5 ANALYSIS

---

### 5.1 MISSING OR IMPLAUSIBLE DATA

Data quality and completeness of the PICANet data is high. Validation visits are undertaken to each unit or transport service approximately every 18 months to inspect data quality of entries in the preceding months. However, data checks on all data will still be completed to investigate for missing or implausible data values.

According to correspondence with ICNARC, data quality of the ICNARC data is believed to be reasonable for the variables requested. The only issue reported at this stage is that certain aspects of the PRISM (paediatric risk of mortality score) score are not collected. The data items and whether they are collected (collected: yes/no) are as follows: SBP (yes); DBP (yes); heart rate (yes); respiratory rate (yes); P/F (yes); PaCO2 (yes); PT/PTT (no); Bilirubin (no); Calcium (no); Potassium (yes); Glucose (yes); Bicarbonate (yes); Pupils (reactivity not size); GCS (yes, if not sedated).

If levels of missing data are high ( $\geq 10\%$ ) for key variables, reasons for this will be investigated (e.g. whether one particular transport team has a certain variable consistently missing – indicating this is not missing at random) and methods to account for this may be used. For example, if we believe that missing PIM scores are probably those of the sickest children, we may propose to undertake a sensitivity analysis to impute poor scores and rerun the initial analyses to assess the impact on the results. Conversely, if we believe data are missing at random we will investigate whether multiple imputation may be appropriate. At this stage we are unaware of the level of missing data which will be encountered. We will develop robust proposals for handling each variable as we become aware of the level of missingness and present these to the Study Management Group for approval before analysis is conducted.

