#### **5.3.5 Sensitivity analyses**

All analyses undertaken will be assessed for their robustness via a thorough sensitivity analysis. These will fall under three types:

1. The impact of unobserved confounding will be investigated using instrumental variables (see below)
2. Assumptions surrounding missing data
3. Assumptions of statistical models

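### Imputing poor PIM scores is not a conservative check: PIM is a confounder, so the fill can leave residual confounding and pull the timeliness odds ratio toward its unadjusted value

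*SAP*

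**What the plan says.** Section 5.1 of the SAP sets a trigger for action on missing data, "If levels of missing data are high", given as 10% or more for key variables. Reasons are then to be investigated. Two branches follow as illustrations:

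- Missingness related to severity: "if we believe that missing PIM scores are probably those of the sickest children", then "we may propose to undertake a sensitivity analysis to impute poor scores and rerun the initial analyses to assess the impact on the results".
- Data believed missing at random: whether multiple imputation is suitable will be looked into.

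The section adds "At this stage we are unaware of the level of missing data which will be encountered" and "We will develop robust proposals for handling each variable as we become aware of the level of missingness". Those proposals need Study Management Group approval before analysis. Section 5.3.5 lists "Assumptions surrounding missing data" as one of three types of sensitivity analysis, without further detail. The table of potential confounders in section 5.3.2 contains severity of illness, as PIM-2/PIM-3 score and its individual variables.

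No value, number of values or method of imputation is given for the poor scores.

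**The concern.** Filling in bad values is a familiar stress test for a missing outcome, where it bounds the result. It does not work that way for a confounder. A child whose true risk differs from the inserted one is adjusted for the wrong severity, and the fitted PIM slope, which is shared with the children who have complete data, is altered. Adjustment for severity becomes incomplete and the exposure OR drifts toward its unadjusted value. The direction of that drift follows the confounding: if sicker children are reached sooner, late arrival looks falsely protective; if they are reached later, it looks falsely harmful.

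At stake is how the check is read. Its purpose is to show whether the timeliness result survives doubts about missing PIM. A shift produced by the fill itself could be taken for fragility, or for an effect that is not there.

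The SAP also ties multiple imputation to the missing-at-random branch only. The branch where data are not missing at random therefore has no stated imputation model and no stated way of carrying imputation uncertainty.

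**Working it through.** **Design figures.** SAP section 4.2 expects "15,000 transports over the three year time window of the DEPICT Study" and 7% 30-day mortality. 0.85 x 15,000 = 12,750 within 3 hours, leaving 2,250 over; this reproduces the SAP split. Power for 7% versus 4% exceeds 99.9% (alpha 0.05 assumed), so the SAP's description of it as adequate is confirmed. The SAP gives no figure for the PIM imputation, so the rest is simulation on stated assumptions.

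**Set-up 1 (all parameters assumed).** L = logit(PIM) ~ N(-3.2, SD 1.3); logit P(death) = -0.05 + 0.95 L; logit P(late) = -1.8 - 0.35 (L + 3.2). The true late-arrival OR is 1.00. Missing PIM is replaced by logit(0.30) and the adjusted model refitted. Two large-sample runs:

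| Missing children | Run A (13% missing, crude OR 0.60) | Run B (12.5% missing, crude OR 0.61) |
|---|---|---|
| mildly sicker (about 12% mortality) | 0.81 | 0.83 |
| much sicker (22% mortality) | 0.90 | 0.92 |
| exactly the sickest | 0.94 | 0.97 |
| complete cases | 0.97-0.99 | 0.97-1.01 |

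The differences of 0.02 to 0.03 between runs are of the order of simulation error. If missingness is unrelated to severity, run B gives 0.78 with the PIM slope down from 0.95 to 0.68, but for data believed missing at random the SAP points to multiple imputation.

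**Scale.** The standard error of the log OR at N = 15,000 is about 0.085. For run A:

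- ln 0.81 = -0.211; 0.211/0.085 = 2.5 standard errors.
- ln 0.90 = -0.105; 0.105/0.085 = 1.2.
- ln 0.94 = -0.062; 0.062/0.085 = 0.7.

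Against the crude ln 0.60 = -0.511, these are 41%, 21% and 12% of the confounding put back, slightly overstated because complete cases in that run were themselves a little below 1.

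**Strength and sign of confounding.** At -0.15 per logit unit the 30% fill gives 0.89 to 0.95, against 0.96 with full data in that run. With the sign of the -0.35 reversed it gives 1.06 to 1.26.

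**Set-up 2 (independent, 600,000 records).** PIM slope 1, SD 1.3, 7% mortality, 15% late, true OR 1, confounding of 0.2 or 0.5 log odds per SD in either direction (0.2/1.3 = 0.15 and 0.5/1.3 = 0.38 per logit unit). With +0.5 per SD and 10% missing (crude OR 1.75, full-data OR 1.00):

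| Mortality in missing | Fill 15%: OR (slope) | Fill 30% | Fill 50% |
|---|---|---|---|
| 15% | 1.120 (0.99) | 1.185 (0.81) | 1.268 (0.61) |
| 28% (exactly the sickest) | 1.113 (1.27) | 1.061 (0.97) | 1.068 (0.73) |

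The slope falls when the fill exceeds the missing children's true risk and rises when it is below it. Across this set-up, when the missing are the sickest or nearly so and the fill is 15-50%, the log OR shifts by 0.02-0.07 (weaker confounding) or 0.03-0.16 (stronger).

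**Does the form of the fill or model rescue it?** In set-up 1, random draws of poor scores between 15% and 60% risk gave 0.75, 0.80 and 0.85 (missing at random, mildly sicker, clearly sicker at 17% mortality). A cubic in PIM with the 30% fill gave 0.80, 0.84 and 0.89, against 0.78, 0.83 and 0.88 with a linear term.

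**The alternative.** Delta-adjusted multiple imputation with a shift near the truth gave 0.96-1.02 in every scenario. When the missing were strongly sicker, shifts of 0 to +0.5 gave only 0.81-0.93, so the range must extend to about +2.

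**The case against.** The strongest reply is that the SAP fixes very little here. The sentence is an example, worded as something the team may propose. It applies only if missingness reaches 10%, its reasons have been examined, and the missing scores are believed to be those of the sickest. PICANet completeness is described as high, so the trigger may never be met, and any proposal needs approval first. All of that stands; it is why this is a request for better wording and not a charge that a faulty analysis has been committed to.

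A reader might infer three stronger things that the document does not support:

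- **That every missing score gets one common value.** The SAP says scores, in the plural, and names no value. Draws of higher scores would also fit. The pull toward the crude OR does not depend on a single value, however, as the random-draw result shows.
- **That the severity slope is always flattened.** It can steepen: 1.27 above, against a true 1.
- **That a large false shift follows even when the missing children really are the sickest.** The shift is smallest in that case, and with the weaker confounding and fills of 15-50% the ORs still round to 1.0 at the SAP's one-decimal reporting.

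Two further points carry some weight. Other candidate confounders (diagnosis, ventilation at referral, prior interventions) could carry part of the severity adjustment, which the simulations leave out. And splines or fractional polynomials are to be considered, although a cubic helped little at the 30% fill. Against this, the SAP's condition is a belief about what is probable, which the missing scores cannot confirm, and the method does worse the further the belief is from the truth.

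**Conclusion.** The concern holds as a weakness in the one method the SAP names for PIM missing not at random. Imputing poor scores for a confounder is not conservative and can leave residual confounding. In the set-ups examined, where missingness depends on severity alone, complete cases stayed at about 0.97 to 1.03, so the fill could do worse than leaving the records out.

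The size is conditional. With 13% missing and confounding of -0.35 per logit unit, a 30% fill turns a true OR of 1.00 into about 0.81, 0.90 or 0.94 as the missing children go from mildly sicker to exactly the sickest. With confounding of -0.15 the bias is small. These figures rest on assumed PIM spread, missing fraction, fill value, and strength and direction of confounding, with PIM as the only confounder. The documents support neither a single forecast of the bias nor a claim that it must be large.

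**What to change.** In section 5.1, replace the poor-score example with delta-adjusted multiple imputation, and refer to it from the missing-data item in section 5.3.5:

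1. Impute logit(PIM) from a model containing the outcome, the timeliness exposure, transport team and all confounders in the analysis model.
2. Add a pre-stated upward shift to imputed values only, for example 0, +0.5, +1 and +2 on the logit scale.
3. Pool by Rubin's rules at each shift.
4. Report the timeliness OR with its 95% interval across the shifts, beside the complete-case result.

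No single shift should be read as the answer, since one far from the truth also biases the OR; the range is the result. The cost is a few sentences of SAP wording and a little analysis time. The change fits the existing step of taking missing-data proposals to the Study Management Group before analysis.

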### 5.2 SUMMARY STATISTICS

Summary statistics will be presented to describe the population including:

- Number of children transferred, n (%)

- Age, mean (SD) and sex, n (%) of transported children
- Characteristics of the transports undertaken, n (%)
  - E.g. grade of team leader; care area of handover; operational times (median, range); interventions prior to or during transport, n (%)
- Interventions during or prior to transport conducted by the retrieval team, n (%)
  - E.g. intubation; CVC insertion; primary intraosseous access; arterial access; inotrope infusion; chest drain; ECMO; adverse events en route.
- Primary diagnosis reason, n (%)
  - E.g. respiratory; neurological; cardiovascular; infection; endocrine/metabolic; haematology/oncology; trauma; other
- Reason for admission, n (%)
  - E.g. bronchiolitis; seizure disorder; asthma; croup; postoperative; diabetic ketoacidosis
- PIM-2/PIM-3 predicted mortality risk, median and range
- PIM-2/PIM-3 predicted mortality risk categorised, n (%):
  - Grouped as <1; 1 to <5; 5 to <15; 15 to <30; 30-100.
- PaO2/FIO2 ratio, n (%)
  - Grouped as: <200; 201-300; >300
- Cardiac arrest before contact with transport team, n (%)
- Died in PICU; died within 30 days of admission to PICU; died within 90 days of admission; died within one year, n (%)
- Length of PICU stay, median numbers of days and range
- Information about daily interventions in the PICU, median days (range)

Whilst they will not form part of the main analysis, we will also report the number of children who die en route, and the median (range) time taken to reach their bedside by the transport team.

The differences between the transport teams in terms of their team composition, demographics they serve and facilities they have available will be described descriptively if possible.

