### 4.1 INCLUSION/EXCLUSION

Data on all children ( $\leq 16$  years old) admitted to PICUs in the England and Wales from 2014 to 2016 following transport by a specialist team will be included. Transport events will be linked with the appropriate admission information and other longer-term outcome data. Some children will be transported and admitted more than once over this time period. Summary statistics will be produced for both admission and for the individual child, and analyses will be undertaken using both approaches and compared. For the analysis at child level, the admission closest to the final event will be used and a variable will be included to indicate if they had previous admissions to PICU.

Exclusions will be made for:

- Transport of adults (age  $>16$  years)
- Transport to an unknown location; no match between transport and admission event; transport performed by non-specialist team; transport performed by neonatal team.

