## 5.3 FORMAL STATISTICAL ANALYSES

### 5.3.1 Outcomes for all analyses

#### Primary outcome:

30-day mortality following PICU admission (following first admission) using data from the Office of National Statistics.

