#### **Model 1: The impact on mortality due to timeliness of access to care in transported children**

Three time frames will be considered when investigating the outcome of mortality and timeliness of access to care:

- Time to arrival at bedside after acceptance (we will investigate this first)

- Time of referral to time of acceptance
- Time of referral to time of admission to PICU

A variable to represent timeliness of access to care will be included to indicate if the transport was made in the desired time frame (e.g. continuous time to arrival or dichotomised using any targets: <3 hours: yes/no) or in groupings of 30 mins (0-30 mins; 30-60 mins; 60-90 mins etc.). Other confounders will be identified and included (see Section 5.3.2). If reasons for delay want to be investigated then the PICANet free text comments fields will be interrogated.

Differences which may exist between the transport teams will be accounted for in all analyses of the primary outcome either via use of logistic mixed models (random effect term for transport team) or logistic models with robust standard errors to account for clustering within transport services. Both of these approaches will give very similar (although not identical) results in terms of the coefficients. The model fit will be assessed to see if consideration of transport team improves the model fit via use of the AIC. If differences between transport teams are of direct interest, a categorical term to indicate the transport team will also be included within the model.

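### The timeliness mortality analysis conditions on surviving to PICU admission, which comes after the exposure, and no planned analysis adds the earlier deaths back

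*SAP*

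**What the plan says.** Section 4.1 defines the cohort as children "admitted to PICUs in the England and Wales from 2014 to 2016 following transport by a specialist team will be included". Among its exclusions is a transport with "no match between transport and admission event".

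Section 5.3.1 gives the primary outcome as "30-day mortality following PICU admission (following first admission) using data from the Office of National Statistics". The secondary mortality outcomes run to PICU discharge, or to 90 days and 1 year after PICU admission, so they too concern admitted children only.

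Model 1 in section 5.3.3 lists three exposures. The one to be studied first is acceptance to bedside arrival: "Time to arrival at bedside after acceptance (we will investigate this first". The second is referral to acceptance. The third is "Time of referral to time of admission to PICU".

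Section 5.2 addresses one group of earlier deaths: "Whilst they will not form part of the main analysis, we will also report the number of children who die en route". For these children it also plans a summary of how long the team took to arrive. Deaths while waiting for the team are not mentioned anywhere.

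Section 5.3.5 names three types of sensitivity analysis: unobserved confounding (by instrumental variables), missing data, and statistical model assumptions.

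**The concern.** In a study of delay, follow-up should start no later than the delay itself. Here the exposure runs first, entry requires a PICU admission, and only then does the outcome clock start. A child who deteriorates and dies because the team came late, or because the whole pathway was slow, contributes neither a death nor a denominator.

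Two things could follow. Deaths caused by delay before admission are lost as events. And if long waits remove the frailest children, those admitted after a long wait are a selected group whose later mortality may look favourable. Either would pull the odds ratio for delay towards, or below, 1. The result is meant to inform national standards of care (Objective 2.3), so an apparently reassuring estimate could be read as evidence that delay does no harm.

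The instrumental-variable analyses do not settle this. They address unmeasured confounding. An instrument that changes delay may also change who survives to be included.

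**Working it through.** **Order of events**

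| Step | Where in the SAP | Position in time |
|---|---|---|
| Referral, then acceptance | Model 1, second exposure | before entry |
| Acceptance to bedside | Model 1, first exposure | before entry |
| Referral to PICU admission | Model 1, third exposure | ends at entry |
| Matched PICU admission required | 4.1 | entry |
| 30-day mortality clock starts | 5.3.1 | at entry |

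Entry and the start of follow-up both fall at or after the end of every exposure. That establishes the structural point without arithmetic.

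**The plan's own figures (section 4.2)**

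- Split: 15,000 × 0.85 = 12,750 reached within 3 h; 15,000 × 0.15 = 2,250 later. Both reproduce.
- Power for 7% versus 4%, assuming two-sided 5% (the SAP states no alpha), with the 12,750 at 7%. The pooled rate is 0.0655. Standard error under the null = √[0.0655 × 0.9345 × (1/12,750 + 1/2,250)] = 0.00566. Standard error under the alternative = √[0.07 × 0.93/12,750 + 0.04 × 0.96/2,250] = 0.00471. z = (0.03 − 1.96 × 0.00566)/0.00471 ≈ 4.0, so power is above 99.9%. It is also above 99.9% with the rates swapped. The claim of adequate power reproduces.
- Expected deaths at 7%: 0.07 × 15,000 = 1,050.

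**What omitted deaths could do to the odds ratio**

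Assume 7% mortality among admitted children in both groups, so the planned crude odds ratio is 1.00. Deaths: fast 0.07 × 12,750 = 892.5; slow 0.07 × 2,250 = 157.5. Survivors: 11,857.5 and 2,092.5. Now add *a* omitted deaths to the fast group and *b* to the slow group. Survivors do not change, so

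OR = [(157.5 + b)/2,092.5] ÷ [(892.5 + a)/11,857.5] = 5.667 × (157.5 + b)/(892.5 + a).

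This equals 1 when b/a = 157.5/892.5 = 0.176, that is, when b/(a + b) = 15%. Above that share the odds ratio rises; below it, it falls.

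The SAP gives no number D of omitted deaths, so D and the slow share are assumptions:

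| D | 0% slow | 15% slow | 50% slow | 100% slow |
|---|---|---|---|---|
| 15 | 0.98 | 1.00 | 1.04 | 1.10 |
| 30 | 0.97 | 1.00 | 1.08 | 1.19 |
| 75 | 0.92 | 1.00 | 1.19 | 1.48 |
| 150 | 0.86 | 1.00 | 1.36 | 1.95 |

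Example, D = 30 all slow: 5.667 × 187.5/892.5 = 1.19. The Woolf standard error of the log odds ratio is √(1/892.5 + 1/11,857.5 + 1/187.5 + 1/2,092.5) = 0.0838, so the 95% CI is 1.01 to 1.40. The smallest number of omitted deaths, all slow, that lifts the lower limit above 1 is 29 (OR 1.18).

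**How firm the 15% is.** In general the break-even is the slow group's share of the deaths that are counted. If admitted mortality were 7% fast and 4% slow, it would be 90/(892.5 + 90) = 9.2%. If 4% fast and 7% slow, it would be 157.5/(510 + 157.5) = 23.6%. So 15% belongs to the equal-mortality case.

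**The case against.** **The population is declared.** Objective 1.1 is worded for children transported to PICU, and sections 4.1 and 5.3.1 follow that wording. Section 5.2 says openly that en-route deaths are left out, and promises their number and time to bedside. This stands. A reader might infer that Objective 1.1 cannot be answered at all. The documents do not support that: the planned analysis answers it for children who reach PICU.

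**The direction is not established.** A reader might infer that the estimate is certainly biased towards no harm. That is plausible but not shown. If the sickest children are reached fastest and some die in transit, the omitted deaths sit in the fast group and the crude shift reverses. Scenarios that assume a higher pre-admission death rate after a late arrival build in the sign. For example, take 0.2% early against 0.5%, 1% or 2% late, with 7% mortality after admission. Mortality is 0.002 + 0.998 × 0.07 = 7.19% early and 7.47%, 7.93% or 8.86% late, giving odds ratios of 1.04, 1.11 and 1.26. With 0.2% in both groups the answer is 1.00; with 0% late it is 0.97. This objection also stands.

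**Not every earlier death is covered by the same text.** Section 5.2 concerns en-route deaths only. A child who dies before the team arrives is outside the cohort through the inclusion rule, and the SAP does not promise even a count. The SAP also does not say that the no-match exclusion is meant as the way to handle deaths. As worded, though, it would remove a transport that ended in death before admission.

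**A full repair is not simple.** A child who dies before team arrival has no completed time to bedside. Severity in the section 5.3.2 table is taken from first contact with the team, so that child also lacks the main confounder. No pre-admission death has a completed referral-to-admission time.

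None of this removes the structural problem. Uncertainty about the direction is a reason to examine it formally, and reporting a count beside an odds ratio does not show what the odds ratio would have been.

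**Conclusion.** The concern holds as a structural point. The mortality analysis of timeliness conditions on survival to PICU admission, an event after the exposure, and no planned sensitivity analysis addresses it. The analysis may understate harm from delay.

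The SAP does not allow a firmer statement. The shift is towards harm only if more than about 15% of the omitted deaths are in the group reached after 3 hours, and it reverses below that share. Across 15 to 150 omitted deaths and every possible split, the crude odds ratio runs from 0.86 to 1.95 where the planned analysis would give 1.00. That range rests on three assumptions: equal 7% mortality after admission, no covariate adjustment or clustering, and a number of omitted deaths that the SAP does not give. If the true number is small, the effect may be negligible.

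**What to change.** For acceptance-to-bedside and referral-to-acceptance, prespecify an analysis that:

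- keeps transports ending in death after team arrival but before PICU admission;
- exempts them from the no-match exclusion in section 4.1;
- counts them as events, with mortality defined from acceptance (or referral) to 30 days after PICU admission.

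This should be at least a sensitivity analysis added to section 5.3.5 and reported beside the admission-based result.

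For deaths before team arrival, and for the referral-to-admission exposure, adding records to the logistic model will not work because the exposure is not completed. State the limitation, and give the count or simple bounds where records allow.

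The cost for the first part is SAP wording and modest recoding, since section 5.2 already plans to summarise time to bedside for en-route deaths. There are three drawbacks. Some of these records will lack PICU-derived covariates, so the adjustment set for this analysis must be fixed in advance. The added deaths may be few. And the analysis still conditions on survival to team arrival: it moves the point of selection earlier but does not remove it.
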